2.3 Study Agent Erlotinib

One approach to block EGFR activity involves the use of small molecules to inhibit tyrosine kinase activity of erbB-1 receptor.⁸⁶⁻⁸⁸ Protein kinases are a family of cellular components that regulate signaling for a wide variety of cellular processes such as growth and differentiation. They are divided into subgroups based on the amino acid

substrate for phosphorylation: serine, threonine or tyrosine. Tyrosine kinase was the last to be identified following the discovery of the Rous sarcoma virus *src* gene approximately 20 years ago. Tyrosine kinase activity is considered a hallmark of the transformation of malignant cells. Substantial evidence *in vivo* and *in vitro* points to the close relationship between tyrosine kinase activity and the initiation, growth and metastases of many human tumors.

Tyrosine kinase is the intracellular domain of the EGFR and the other members of the *erbB* family except the *c-erbB-3*. As such, it serves as the first step in the EGF signal transduction pathway. The binding of a ligand to the extracellular domain of EGFR activates the intrinsic tyrosine kinase activity, which then, transfers the terminal phosphate group of adenosine triphosphate to the hydroxyl group of specific tyrosine residues of target proteins and of the receptors themselves. Tyrosine kinase has several protein substrates, PLC- γ 1, PI-3 kinase, GAP, MAP kinase, *raf* kinase, and lipocortin I. Although growth factors and their receptors vary in structure, tyrosine kinase activity remains the initial step in the mechanism of action for all growth factors. The discovery of small molecules that interfere with ATP binding or utilization represented a major breakthrough in tyrosine kinase-targeted therapy. In the last two decades, enormous efforts have been made to develop compounds that can inhibit tyrosine kinase activity and several kinase inhibitors have been generated and successfully inhibited cell cycle progression and induced apoptosis in both human tumor cell lines *in vitro* and in xenograft models. Inhibitors bind intracellularly to EGFR tyrosine kinase, inhibit kinase activity, and subsequently block the signal transduction cascade. Tyrosine kinase inhibitors (TKIs) targeting the intracellular domain are small molecules that specifically inhibit EGFR tyrosine kinase activity over precise dose ranges. Several different classes of TKIs have been reported after molecular modeling has been employed to develop compounds that can selectively and tightly bind to various kinase targets. The quinazolines and the pyridopyrimidines currently appear to be the most promising classes of the TKIs.

Erlotinib (OSI-774, TarcevaTM) is an orally bioavailable EGFR TKI low-molecular weight quinazoline derivative. This novel drug induces cell cycle arrest at the G1 phase and has a high specificity as an inhibitor of the EGFR tyrosine kinase. Erlotinib acts through direct and reversible inhibition of EGFR tyrosine kinase.⁸⁹ Erlotinib inhibits human EGFR tyrosine kinase with an IC₅₀ of 2 nM (0.79 ng/mL) in an *in vitro* enzyme assay and reduces EGFR autophosphorylation in intact tumor cells with an IC₅₀ of 20 nM (7.9 ng/mL). This inhibition is selective for EGFR tyrosine kinase in assays of isolated tyrosine kinases and cellular assays. EGFR is overexpressed in a significant percentage of epithelium-derived carcinomas. Erlotinib inhibits the EGF-dependent proliferation of cells at nanomolar concentrations and blocks cell cycle progression at the G1 phase. Oral administration of erlotinib to mice reduced the level of EGFR autophosphorylation in human tumor xenografts by > 70% for more than 12 hours.⁹⁰ Daily administration of erlotinib markedly inhibited the growth of HN5 human head and neck tumors and A431 squamous cell carcinoma xenografts in athymic mice, with near complete inhibition of tumor growth during a 20-day treatment regimen at the highest doses. Many other potential effects of erlotinib in oral cancer prevention and therapy, including the abrogation of EGFR-dependent induction of COX-2 are discussed above in Section 2.2. Erlotinib also has been shown to downregulate cyclin D1,⁶⁷ which is upregulated in head and neck IEN and has been reduced by other agents in preventing head and neck carcinogenesis.⁴⁹

[figure not shown]
As of February 2005, erlotinib has been studied clinically in more than 6,800 healthy subjects and cancer patients (excluding patients exposed to placebo) in a number of Phase I, II and III studies, including a large phase II study showing modest single-agent activity in advanced squamous cell carcinoma of the head and neck.^{91,92} Erlotinib/Tarceva was approved by the US FDA for second- and third-line treatment of advanced or metastatic NSCLC at a dose of 150 mg daily.⁷⁹

Following oral administration in rats and dogs, erlotinib was rapidly absorbed (T_{max} 1 to 2 hours) with an oral bioavailability of 45% to 88%. Erlotinib displayed nonlinear pharmacokinetics, with greater than expected increases in C_{max} and AUC with increasing doses. Repeat-dose studies showed no substantial changes in the pharmacokinetics of erlotinib over time. In vitro measurement of protein binding of erlotinib in animal and human plasma ranged from 85% to 95%. The primary route of metabolism was oxidation by CYP3A4. Erlotinib and its metabolites were excreted predominantly via the feces (> 90%) with a small amount recovered in urine.

Toxicology studies were conducted in mice, rats (up to 6 months), dogs (up to 1 year), and monkeys (1 week). Treatment-related effects observed in at least 1 species or study included effects on the cornea (atrophy and ulceration), skin (follicular degeneration and inflammation, redness, and alopecia), ovary (atrophy), liver (liver necrosis), kidney (renal papillary necrosis and tubular dilatation), and gastrointestinal tract (delayed gastric emptying and diarrhea). Red blood cells (RBC) parameters were decreased, and white blood cells (WBCs) primarily neutrophils, were increased. There were treatment-related increases in alanine aminotransferase (ALT), aspartate aminotransferase (AST), and bilirubin; increases in bilirubin were likely caused by treatment-related impairment of bilirubin metabolism.

3. SUMMARY OF STUDY PLAN

The proposed study will be a double-blinded, placebo-controlled randomized study to evaluate the chemopreventive effect of erlotinib in a high-risk group of oral IEN patients. The trial will be conducted at five centers in the United States: M. D. Anderson Cancer Center, Memorial Sloan-Kettering Cancer Center, Emory University, the University of Chicago, and the University of Maryland. There will be two categories of high-risk patients in this study: (a) loss of heterozygosity (LOH) at 3p14 and/or 9p21 in the oral IEN of patients with a history of curatively treated oral cancer and (b) LOH at 3p14 and/or 9p21 plus at one other chromosomal region in the IEN of patients with no oral cancer history. The trial will randomize 150 patients--75 will receive erlotinib (150 mg po QD) and 75 will receive matched placebo (po QD). The trial period is 4.5 years (including one-year treatment)--2 years to complete accrual and 2.5 more years of follow-up (mean of the additional follow-up period from 1.5 to 3.5 years). A summary of the study schema appears below:

Once at the study site, informed consent will be obtained from willing participants, medical history will be obtained, oral lesions (if present) will be examined, blood samples will be taken, collection of archival tissue sample or biopsy of oral leukoplakia lesions for LOH analysis, and the epidemiologic and nutrition questionnaire (included in Appendix A) will be initiated. Patients classified with oral leukoplakia and LOH with or without a prior history of cured oral cancer will be eligible for inclusion in the study and will be randomized into one of two groups.

The primary endpoint of the trial will be the oral cancer-free survival in patients receiving erlotinib as compared with the control group. Multiple secondary endpoints will be assessed as outlined in Section 1.2.

4. PARTICIPANT SELECTION

4.1 Inclusion Criteria

All the following conditions must be met before a patient can be included in the study:

4.1.1 Male or female patients with one of the following: (a) loss of heterozygosity (LOH) at 3p14 and/or 9p21 in the oral IEN of patients with a history of curatively treated oral cancer or (b) LOH at 3p14 and/or 9p21 plus at one other chromosomal region in the IEN of patients with no oral cancer history.

4.1.2 Participants must have confirmed diagnosis of oral IEN lesion with LOH. (Note: The initial screening biopsy of oral IEN lesion with LOH must be obtained within 12 months of study enrollment. If initial diagnostic biopsy for LOH is > 3 months prior to study enrollment, investigators may use clinical judgment to order an additional screening biopsy to assess histopathological changes).

4.1.3 Age \geq 18 years

4.1.4 ECOG performance status < 2

4.1.5 Participants must have normal organ and marrow function as defined below within 30 days of randomization:

CBC with differential white cell count – acceptable results must include:

WBC \geq 3,000/ μ l, hemoglobin \geq 10 g/dl, platelet count \geq 125,000/ μ l

LFTs - total bilirubin and alkaline phosphatase, AST (SGOT) and ALT (SPGT) all within \leq 1.5xULN. Note: At the discretion of the attending physician, participants with Gilbert's disease may still be eligible to participate in the event the total bilirubin value is > 1.5xULN.

Kidney function - serum creatinine \leq 1.5xULN

Chemistry - Sodium and potassium all within normal institutional limits.

4.1.6 The effects of the study agent on the developing human fetus are unknown. For this reason, women of child-bearing potential and men must agree to use adequate contraception (hormonal or barrier method of birth control; abstinence) prior to study entry and for the duration of active treatment. Negative serum pregnancy test in women of child-bearing potential. Childbearing potential will be defined as women who have had menses within the past 12 months, who have not had tubal ligation or bilateral oophorectomy. Should a woman become pregnant or suspect she is pregnant while participating in this study, she should inform her study physician immediately.

4.1.7 Ability to understand and the willingness to sign a written informed consent document

4.2 Exclusion Criteria

- 4.2.1 Patients with active cancer or any cancer within the previous two years, excluding oral and non-melanoma skin cancer.
- 4.2.2 Patients with acute intercurrent illness or who have had surgery, radiation therapy, or chemotherapy within the preceding 4 weeks unless they have fully recovered.
- 4.2.3 Patients with a documented history of coagulopathy and/or those taking warfarin or warfarin-derivative anticoagulants
- 4.2.4 Women who are pregnant (confirmed by β -HCG if applicable) or breastfeeding
- 4.2.5 Any medical or psychological condition or any reason that, according to the investigator's judgment, makes the patient unsuitable for participation in the study
- 4.2.6 Patients who have participated in other experimental therapy studies within 3 months of enrollment to this trial
- 4.2.7 Patients with a history of inflammatory bowel disease
- 4.2.8 Patients with a documented history of interstitial lung disease

4.3 Inclusion of Women and Minorities

No patient will be excluded from the study on the basis of ethnicity, race, sex, or older age. Most oral cavity cancers arise in patients above the age of 65, but the incidence in younger patients is increasing, i.e. including patients younger than 50 years. The study subjects will be patients above 18 years of age, since oral IEN/cancer is extremely rare in children and the safety profile of erlotinib is unknown in this age group. Efforts will be made to recruit all minority participants identified with IEN and LOH.

4.4 Recruitment and Retention Plan

Methodology, Infrastructure and Accrual

The 20-years experience of M. D. Anderson Cancer Center (MDACC) in advancing the translational study of head and neck cancer chemoprevention in the settings of head and neck IEN and SPTs^{1,2,4,38,93-102} includes 9 trials in oral IEN, the majority of which were randomized, controlled and 5 of which were completed within the past 5 years. With this experience, MDACC has established effective methodologies and a strong clinical, laboratory and accrual infrastructure for translational head-and-neck chemoprevention. The majority of trial patients will be accrued at MDACC, with additional accrual from Memorial Sloan Kettering Cancer Center, Emory University, the University of Chicago, and the University of Maryland. The estimated accrual figures for all participating centers are presented in Table 1 (relevant data and calculations follow the table):

Table 1. Screenings and Randomizations by Quarter (Q).

	Year 1				Year 2				Year 3
	Q1*	Q2†	Q3	Q4	Q1	Q2	Q3	Q4	Q1‡
Screened	26	59	72	72	59	59	59	59	26
Randomized	8	18	22	22	18	18	18	18	8

* M. D. Anderson alone (while awaiting IRB approval at the 4 other sites); begins with MDACC protocol activation.

† The 4 other sites join M. D. Anderson in this quarter.

‡ Total for 4 other sites; M. D. Anderson finished at end of Year 2.

Quarter 1 (Q1) screenings (26) and accruals (8) in the table reflect trial activation at MDACC alone while the protocol is undergoing IRB review and approval at the other 3 clinical sites. These sites begin screening and accrual in Q2 of Year 1 and will complete accrual in Q1 of Year 3. Each center will have a substantial cohort of potentially eligible patients in follow-up when the trial is activated. These patients will be captured (along with new patients) throughout the first year at each center. We assume that 2/3 of the patients will have oral intraepithelial neoplasia (IEN) and a prior oral cancer and 1/3 will have oral IEN alone (no oral cancer history). Among those with a prior cancer, 67% will have eligible LOH and 60% of these will consent to go on trial. Therefore, the randomization “yield” among screening patients with oral IEN and a prior oral cancer is $0.67 \times 0.60 = 0.40$. On the other hand, among patients with oral IEN alone, 28% will have eligible LOH and 45% will consent to go on trial. The randomization “yield” of these patients is $0.28 \times 0.45 = 0.13$. Therefore, the overall yield is $0.67 \times 0.40 + 0.33 \times 0.13 = 0.31$. Based on these assumptions, we will screen approximately 491 patients in order to accrue 150 randomized patients at all 4 participating U.S. clinical sites.

Accrual at MDACC

There are no competing studies for the oral IEN patients in this study at M. D. Anderson Cancer Center, and the trial has the full support of the chairs of the departments of Thoracic/Head and Neck Medical Oncology and Head and Neck Surgery (which includes dental oncology). As part of this collaboration, we have added this clinical protocol to an interactive database managed by the department of Head and Neck Surgery entitled "First Match." This matching database will alert research personnel of new patients with certain characteristics, i.e., oral cancer diagnosis, that have been evaluated in the Head and Neck Surgery clinic. Through this mechanism, these patients may then be approached at the time of their follow-up visit to discuss possible participation in this clinical trial.

Oral IEN/LOH Patients with Curatively Treated Cancer History: MDACC sees 300 oral cancer patients per year (actual average in past 5 years = 309), who are referred primarily by dentists and ear, nose and throat (ENT) specialists. The eligible patients in this cohort are not eligible for any other protocols, have no standard treatment, and are continually followed by M. D. Anderson Cancer Center surgeons over the years. These IEN with oral cancer history estimates are a collaboration of Drs. [name] (Chair, Thoracic/Head and Neck Medical Oncology), [name] (Chair, Head and Neck Surgery), and [name] (head and neck surgeon), and the Head and Neck Center database manager.

Oral IEN/LOH Patients with No Cancer History: Patients with eligible IEN (based on LOH) and no history of cancer also have no standard treatment. Approximately 80 oral IEN patients (no cancer history) are registered within our current follow-up program within our Head and Neck Cancer SPORE and are available for recruitment to our trial. We also evaluate approximately 50 new oral IEN (no prior cancer) patients per year in the MDACC Head and Neck Center. Screened patients who do not have the eligible LOH profile will be followed observationally (and prospectively) with biopsy as indicated to assess acquisition of LOH; if LOH is acquired, these patients become eligible for the trial. Furthermore, our head and neck team will move in Summer 2006 into a new Head and Neck Center, where Drs. [name] and [name] will establish a comprehensive oral premalignancy/IEN program since oral IEN is a major research focus of both of their departments.

Accrual at the University of Chicago, Memorial Sloan Kettering, Emory University, and the University of Maryland

As does MDACC, our four partner accrual centers all have pre-eminent programs of head and neck cancer therapy and prevention practice and research, including active programs of chemoprevention in oral IEN. The considerations for estimating accrual at each center are similar to those outlined above for MDACC. The conflicts between this trial and other trials are from none to minimal at these respective centers, and their accrual estimates have taken into account the portfolio of trials at each center.

The University of Chicago Head and Neck program is a world renowned program with published experience in oral IEN trials.^{1,80,82,103} The collaborative history of MDACC with the University of Chicago includes a targeted-agent trial in oral IEN.¹⁰³ Co-investigator [name], who will lead our clinical trial at the University of Chicago, is an expert in the area of EGFR targeting in clinical/translational trials in head and neck cancer. Memorial Sloan Kettering has an outstanding Head and Neck cancer program and collaborates already with MDACC in our NCI N01 cancer chemoprevention consortium. Co-investigator [name] is a leader in targeted prevention in oral IEN¹⁰⁴ and will lead our clinical trial at Memorial Sloan Kettering. [name] is PI of an N01 trial of an PPAR-gamma agonist in oral IEN and is a key collaborator with MDACC on the recently completed RCT of celecoxib in oral IEN. Emory University also has strong experience in head and neck cancer therapy and prevention under the leadership of Co-investigator [name], who is Director of the Clinical and Translational Cancer Prevention Program at Emory. [name] has extensive experience in clinical/translational trials in oral IEN and in the setting of curatively treated head and neck cancer patients and has long-standing collaborations with head and neck investigators at M. D. Anderson Cancer Center, where he was a highly respected member of the faculty.^{52,84,95,105,106} [name] is one of the key architects for the current prevention trial and the key player for development of the genetic test used for selection of high risk patients in the clinical trial. [name] has recently moved to University of Maryland Dental School to serve as Professor and Chairman, Department of Oncology and Diagnostic Sciences.

LOH Screening

Based on the strong data presented above in Molecular Risk and Cohort Selection, the previous section, we propose to use LOH status to select patients to participate in our prevention trial. There will be two selection criteria. IEN

patients with no oral cancer history must have LOH at 3p14 and/or 9p21 plus at least one of the following regions: 17p, 8p, 11p, 4q, or 13q. IEN patients with clinically cured oral cancer must have LOH at either 3p14 and/or 9p21 to be eligible for the study.

[name] extensive data derived from small paraffin-embedded tissue samples of oral IENs and oral cancers demonstrate that using 2-3 microsatellite markers for each locus gives a > 95% informative test rate (deletion status could be interpreted). We will use automatic capillary DNA analyzer (AB3100) to separate microsatellite alleles and to quantify peak heights of each alleles. LOH is defined as the ratios of the peak heights of the two alleles in lesion (L1/L2) DNA and in the corresponding normal lymphocytes (N1/N2) DNA ≥ 1.43 or 0.7 . The extensive experience of Drs. [name] and [name] in this area of research ensures peak efficiency in the patient screening and selection process. We have established that the LOH status of oral IENs can be determined within 7 business days, which will ensure timely enrollment of patients into our clinical trial.

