Oral cancer development is a multifocal process due both to multiclonal development and clonal intraepithelial spread.^{2,4,14-16} Multifocality likely is a major cause of the failure of local treatment of oral IEN in preventing oral cancer and supports the testing of systemic therapy with agents targeting signaling pathways relevant to oral carcinogenesis such as the EGFR pathways.

Head and neck carcinogenesis is a multistep process requiring the accumulation of multiple genetic alterations.^{1,4,17-27} Extensive genetic analysis of oral cancers and oral IEN has identified many common genetic abnormalities. LOH, a result of genetic instability and clonal selection, is one of the major mechanisms to inactivate tumor suppressor genes. Our earlier study showed that IEN with LOH at 3p14 and/or 9p21 regions increases the IEN risk for developing invasive oral cancer.¹⁹ The 3-year oral cancer incidence in the LOH group was approximately 25%. The region 3p14 contains the tumor suppressor gene FHIT, and 9p21 contains the tumor suppressor genes p16/p15/p14, supporting the hypothesis that clones with deletions at these chromosomal

regions are more advanced in the tumorigenic process. Several subsequent studies by other groups had similar results and conclusions.^{20,21,23-26}

Rosin *et al.* employed their centralized Oral Biopsy Service and the database of the British Columbia Cancer Registry to identify 116 patients who had oral IEN and who had been followed for a long period.²³ Importantly, only patients whose oral lesions had moderate histological changes (hyperplasia or mild or moderate dysplasia) similar to our earlier study¹⁹ were selected for the study. The 3-year oral cancer incidence in the 3p14 and/or 9p21 LOH group was remarkably similar (25%) to our earlier study. A substantial proportion of lesions with LOH at 3p14 and/or 9p21 did not develop oral cancer, and so this group investigated the additional chromosomal loci 4q, 8p, 11q, 13q, and 17p, which are commonly deleted in oral cancers.²³ They found that LOH at one of these additional loci plus at 3p14 and/or 9p21 significantly improved the ability of LOH to predict oral cancer development. The 3-year cancer rate was 35%, and this expanded LOH profile was found in approximately 28% of the oral lesions. Several tumor suppressor or candidate tumor suppressor genes, such as TRAIL-R1 and TRAIL-R2 at 8p21.3 and p53 tumor suppressor gene at 17p13, are located in these chromosomal regions.

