The Epidemiologic Questionnaire Database will contain entered data from completed epidemiologic and nutrition questionnaires. Hard copies of the epidemiologic and nutrition questionnaires will be filled out during an interview initiated at baseline and at the completion of the follow-up period. Participants at University of Chicago, Memorial Sloan-Kettering, Emory University – Winship Cancer Institute, and the University of Maryland will submit the original questionnaires to [name] at the following address to be edit checked and entered into the Epidemiologic Questionnaire Database:

[name]
U.T. M. D. Anderson Cancer Center
Department of Epidemiology
[name]
Houston, Texas 77030

The original will be stored in a locked file at M. D. Anderson Cancer Center following data entry.

Blood and Tissue Samples

If initial diagnostic tissue sample for LOH is > 12 months prior to study enrollment or unavailable, a biopsy sample will be taken from at least one existing lesion. Biopsy samples may be taken from all existing lesions at the discretion of the attending physician. The biopsies should be a minimum of 4-5 millimeters in diameter. If the entire lesion is excised at baseline, subsequent biopsies will be performed on normal appearing mucosa at the same site as clinically indicated. The biopsies will be partitioned for snap freezing and for fixation in 10% formalin immediately. Please note: Archival diagnostic tissue specimens obtained for LOH analysis will not be processed for snap freezing. All biopsy specimens (initial screening biopsy for LOH analysis and subsequent biopsy specimens) from Memorial Sloan Kettering Cancer Center, Emory University, University of Chicago, and the University of Maryland will be **ONLY** prepared for fixation (see Appendix G).

[figure not shown]
LOH investigations are performed on at least one sample taken (see “LOH Screening” section for details).

Blood - 10 cc's of blood (1-5cc EDTA tube and 1-5cc SST tube) will be drawn at each baseline, on-study and follow-up visit for analysis of routine laboratory parameters as listed in Section 7. 40 cc's of blood (3-10 cc heparinized tubes and 1-10cc EDTA tube) will be drawn at the pre-study blood draw for isolation of lymphocytes. 10 cc's of blood (1-10cc EDTA tube) will also be drawn at specified on-study visits for biomarker analysis and plasma trough levels.

Blood samples and biopsy specimens will be collected and shipped as detailed in Appendix G.

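### The LOH Screening rule for patients with no oral cancer history names 11p, but the only data on additional loci, the source of the 35% rate and 28% yield, are for 11q

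*Combined protocol and SAP*

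**What the plan says.** **The rule.** Section 4.4, LOH Screening, sets two selection criteria. Patients with clinically cured oral cancer need loss at 3p14 and/or 9p21 only. Patients without prior oral cancer "must have LOH at 3p14 and/or 9p21 plus at least one of the following regions: 17p, 8p, 11p, 4q, or 13q".

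**Its stated basis.** The same paragraph opens: "Based on the strong data presented above in Molecular Risk and Cohort Selection, the previous section, we propose to use LOH status". No heading of that name appears in the text available.

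**The data.** Section 2.1 (Multifocal, Multistep Carcinogenesis) describes a cohort of 116 patients in which "this group investigated the additional chromosomal loci 4q, 8p, 11q, 13q, and 17p, which are commonly deleted in oral cancers". For loss at one of these loci on top of 3p14 and/or 9p21 it reports: "The 3-year cancer rate was 35%, and this expanded LOH profile was found in approximately 28% of the oral lesions".

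**Where those figures are reused.** The accrual plan in section 4.4 assumes that "among patients with oral IEN alone, 28% will have eligible LOH and 45% will consent to go on trial". Section 12.2 uses the 28% yield again in assumption 2 and takes 35% as the IEN-alone control rate in assumption 3.

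**Other eligibility text.** Criterion 4.1.1(b) requires "LOH at 3p14 and/or 9p21 plus at one other chromosomal region in the IEN of patients with no oral cancer history" and names no region. The section 3 summary is worded the same way. Section 1 speaks of one further specific locus, also unnamed. Section 7.7, Blood and Tissue Samples, points back to the list: "LOH investigations are performed on at least one sample taken (see “LOH Screening” section for details").

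**The concern.** Eligibility in the IEN-alone stratum is decided by a molecular profile, so the list of regions is the entry criterion. One entry differs from the panel that supplies the stratum's planning figures, and it has no support elsewhere in the protocol.

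Two things follow if the list is applied as written. First, patients are sorted differently from the cited data: someone whose only additional loss is at 11q is refused, and someone whose only additional loss is at 11p is admitted. Under section 4.4, screened patients without the eligible profile are followed observationally, and "if LOH is acquired, these patients become eligible for the trial". A refused 11q patient would therefore wait for a further loss that the cited panel would not have required. Second, the 35% three-year rate and the 28% yield were not derived for the list as it stands.

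Allocation happens after eligibility is settled, so the comparison between arms is not biased. What is at stake is who enters the stratum and whether the planning figures describe them.

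**Working it through.** **1. The two lists side by side**

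| Region | Section 4.4 rule | Section 2.1 data |
|---|---|---|
| 4q | yes | yes |
| 8p | yes | yes |
| 13q | yes | yes |
| 17p | yes | yes |
| Chromosome 11 | **11p** | **11q** |

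11p occurs nowhere else in the document, and neither a rate nor a prevalence is given for it.

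**2. Reproducing the plan's power**

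Inputs from section 12.2: 100 prior-cancer and 50 IEN-alone patients, 1:1 allocation, uniform accrual over 2 years, analyses at 2.5, 3.5 and 4.5 years at levels 0.0005, 0.014 and 0.045, and 10% loss to follow-up with uniform timing.

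Hazards follow from λ = −ln(1 − p)/3:
- prior cancer, control: −ln(0.35)/3 = 0.3499
- prior cancer, erlotinib: −ln(0.61)/3 = 0.1648
- hazard ratio: 0.1648/0.3499 = 0.471
- IEN alone, control: −ln(0.65)/3 = 0.1436
- IEN alone, erlotinib: 0.1436 × 0.471 = 0.0676

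All agree with the protocol. I simulated the log-rank test stratified by prior cancer (site not modelled) with 40,000 trials per scenario, Monte Carlo standard error about 0.2 points. Power is **86.3%** with 68.8 expected events, 14.4 of them in the IEN-alone stratum. The protocol states 85%.

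**3. Power if some IEN-alone patients qualified on 11p alone**

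The documents do not give the share of IEN-alone patients whose only additional loss is on chromosome 11, or the risk of an 11p-only patient. Both are assumed:
- share: 10% to 30% of 50, that is 5 to 15 patients
- three-year risk: 15% to 25%. Section 2.1 gives 25% for 3p14 and/or 9p21 loss regardless of additional loci.

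Hazards are −ln(0.75)/3 = 0.0959 and −ln(0.85)/3 = 0.0542, with the hazard ratio held at 0.471.

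| Share | 3-year risk | Power | Expected events |
|---|---|---|---|
| none | – | 86.3% | 68.8 |
| 10% | 25% | 86.0% | 68.4 |
| 10% | 15% | 85.3% | 68.0 |
| 30% | 25% | 85.5% | 67.5 |
| 30% | 15% | 84.6% | 66.4 |

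As a separate check, lowering the control rate of the whole IEN-alone stratum to 25% gives 84.4% power and 64.6 events (10,000 trials). Power moves little because 68.8 − 14.4 = 54.4 of the expected events come from prior-cancer patients.

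**4. Screening if 11q-only patients were refused**

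Number to screen = 50/(yield × consent):
- plan's rates: 50/(0.28 × 0.45) = 397. Section 12.2 gives 365 after its own allowance for patients re-approached in year 2.
- 10% of qualifying profiles refused: 50/(0.28 × 0.9 × 0.45) = 441
- 30% refused: 50/(0.28 × 0.7 × 0.45) = 567

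The last two are upper figures, because they add back no patient on 11p. They are a different scenario from step 3 and should not be combined with it.

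**The case against.** **It may be a reading fault.** The difference is one letter in text extracted from a PDF, and 11q itself occurs only once. That is fair: the documents cannot show which occurrence is wrong or why. It affects the cause, not the need to reconcile, and it is why the fix begins with the source pages.

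**The cited section cannot be seen.** The rule refers to a heading that is not in the text, so its data might have differed. This also stands as a caution. Section 2.1 is nevertheless the only place with data on additional loci, and its 35% and 28% are the figures that the plan uses.

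**Criterion 4.1.1(b) is the formal criterion and names no region, so an 11q patient would qualify.** The better reading is that it abbreviates the section 4.4 list: section 1 refers to one specific further locus, section 4.4 says what patients must have, and section 7.7 sends the reader there. If 4.1.1(b) is taken literally instead, it admits any region and conflicts with section 4.4. Either way the text needs correcting.

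**The consequences are small and rest on assumed shares.** True of power, and conceded. The ranges show only that the sample size is not threatened. A selection rule that contradicts its own evidence should still be corrected.

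**Conclusion.** The concern holds. The only list that names the qualifying additional regions differs in one entry from the only panel with data, and nothing in the protocol supports that entry. A one-letter error is the likely explanation, though the documents alone cannot prove it.

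The exposure is limited. Among randomised patients, only the planned 50 IEN-alone patients of 150 can be affected, and of those only patients whose sole additional loss is on chromosome 11. Under the assumed shares and risks, power falls by 86.3 − 84.6 = 1.7 points at most. If 11q was intended, no planning figure changes. If 11p was intended, the 35% and 28% lack a basis for the panel in use. It should be fixed because it is an eligibility rule, not because power is in danger.

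**What to change.** - Check the source pages of sections 2.1 and 4.4 and the LOH laboratory's marker list, then reconcile the two lists.
- If the cited panel is intended, change 11p to 11q under LOH Screening.
- If 11p is intended, state its basis and say that the 35% rate and 28% yield were not derived for that panel.
- Have criterion 4.1.1(b) refer to the one named list, and correct the reference to the heading that does not appear.
- If screening has begun, check whether any IEN-alone patient was accepted or refused on chromosome 11 alone.

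The cost is a short text amendment to LOH Screening and 4.1.1(b), plus one check of laboratory and screening records. Sample size and analysis are unchanged.
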